## 5.1.11. Saliva Collection

Saliva collection should occur at a study visit scheduled in the morning. Subjects should refrain from food intake, drinking liquids and using oral hygiene products for at least 1 hour prior to saliva collection. Prior to collection, the subject will rinse their mouth with water for 1 minute. After resting for a period of 5 minutes subjects will lean forward and hold their head down over a collection tube to initiate a passive drool. Saliva is collected over a period of 20 minutes or until 5 mL is obtained, whichever comes first. Saliva will be processed as described in the S4 Laboratory Manual. All research samples will be sent frozen to a central biorepository to be stored for analysis of  $\alpha$ -syn species. Samples will be made available to researchers with expertise in  $\alpha$ -syn assays to conduct these analyses. Remaining samples may be used to evaluate other proteins, analytes or potential biomarkers. Subjects will not receive any individual results of analysis or testing conducted on the saliva samples.

### 5.1.12. Skin Biopsy

Skin punch biopsies will be performed under local anesthesia (lidocaine) on the cervical paravertebral region and distal thigh to evaluate for  $\alpha$ -syn deposits in skin nerve fibers. Approximately 2 biopsies will be obtained at each location (See S4 Procedure Manual for details regarding the skin biopsy procedure). Skin samples will be processed in formalin as described in the S4 Laboratory Manual and shipped to the central biorepository for storage and analysis of  $\alpha$ -syn species. Immunohistochemistry for  $\alpha$ -syn will be performed by histopathology experts using currently available immunostains and techniques. Remaining samples may be used to evaluate other proteins, analytes or potential biomarkers. Subjects will not receive any individual results of analysis or testing conducted on the skin samples. Subjects will be contacted by phone at 7 days ( $\pm 2$  days) following the procedure to assess for any AEs.

### 5.1.13. Colon Tissue Collection

Colonic submucosa will be biopsied by unprepped flexible sigmoidoscopy with or without sedation (See S4 Laboratory Manual for details regarding the colon biopsy procedure). Approximately 8 samples will be obtained from the sigmoid colon of each subject. Samples from each subject will be fixed in formalin as described in the S4 Laboratory Manual and shipped to the central repository for storage and analysis of  $\alpha$ -syn species. Immunohistochemistry for  $\alpha$ -syn will be performed by histopathology experts using currently available immunostains and techniques. Remaining samples may be used to evaluate other proteins, analytes or potential biomarkers. Subjects will not receive any individual results of analysis or testing conducted on the colonic samples. Subjects will be contacted by phone at 7 days ( $\pm 2$  days) following the procedure to assess for any AEs.

## 5.1.14. Submandibular Gland Tissue Collection

Submandibular gland biopsies will be obtained using a 16-gauge needle under local anesthesia (lidocaine) and optional ultrasound guidance. Up to 4 attempts of needle core biopsies will be performed in each subject. The biopsies will be performed unilaterally through a single puncture site for all biopsies. Tissue will be fixed in formalin as described in the S4 Laboratory Manual and shipped to the biorepository for storage and analysis of  $\alpha$ -syn species. Immunohistochemistry for  $\alpha$ -syn will be performed by histopathology experts using currently

available immunostains and techniques. Remaining samples may be used to evaluate other proteins, analytes or potential biomarkers. Subjects will not receive any individual results of analysis or testing conducted on the submandibular gland samples. Subjects will be contacted by phone at 7 days ( $\pm 2$  days) following the procedure to assess for any AEs.

### 5.1.15. Safety Assessments

### 5.1.15.1. Medical History

Medical and family history, as well as a complete physical and neurological exam will be captured on all subjects at Screening.

### 5.1.15.2. Adverse Events

A clinical AE is any untoward medical occurrence in a subject undergoing procedures as a participant in a clinical trial, without regard to the possibility of a causal relationship. Study site personnel will record the occurrence and nature of each subject's pre-existing conditions. During the study, site personnel will record any change in the condition(s) and the occurrence and nature of any AEs that occur during the reporting periods, which occur 7 days (±2 days) after each of the following procedures: DaTSCANTM, LP, skin biopsy, colon biopsy and submandibular gland biopsy. Site Investigators will document their assessment of the potential relatedness of each AE to study procedures or imaging agent administration via an AE form.

### 5.1.15.3. Clinical Laboratory Assessments

A complete blood count (CBC), Chemistry-20 panel, and PT/PTT will be obtained at screening visit as noted on the schedule of activities. These laboratory assessments will be analyzed by the local laboratory at each of the sites. For females of childbearing potential, a serum pregnancy test will be conducted at screening and a urine pregnancy test (urine dipstick) at the DaTSCANTM imaging visit prior to injection with the radioligand.

In the case where a laboratory value is outside the reference range for the center at screening, a decision regarding whether the result is of clinical significance or not shall be made by the Site Investigator and shall be based, in part, upon the nature and degree of the observed abnormality. The assessment may be repeated once (for the purpose of inclusion) and in any case, prior to enrollment, to rule out laboratory error. In all cases, the Site Investigator will document the clinical considerations (i.e., result was/was not clinically significant and/or medically relevant) in allowing or disallowing the subject to continue in the study.

The laboratory testing will be made available to the practitioners that will be performing the procedures (LP, skin biopsy, colon biopsy and submandibular gland biopsy).

### 5.1.15.4. Vital Sign Measurement

Analysis of safety parameters will include vital signs (blood pressure, heart rate, respiratory rate and temperature) at screening. In addition, vital signs (blood pressure, heart rate, respiratory rate and temperature) will be completed for safety purposes prior to initiation and at completion of the following procedures: DaTSCANTM, LP, skin biopsy, colon biopsy and submandibular gland biopsy.

### 5.1.15.5. Electrocardiogram

The recording of a standard 12-lead ECG will be performed. A paper print-out of the ECG will be made and stored with the source documents at the sites. All ECGs must include the following information: paper speed, voltage calibration, lead identification for each lead, study number, subject number and date of birth, date and time of recording, and Site Investigator's signature following review of the ECG. The ECG will be interpreted locally. In all cases, the Site Investigator will document, the clinical considerations (i.e., result was/was not clinically significant and/or medically relevant) in allowing or disallowing the subject to participate in the procedures for this study. Paper ECGs may be subject to a study-specific central re-evaluation by an external cardiologist or a central ECG laboratory.

### 5.1.15.6. Physical examination

A complete physical examination will include the examination of general appearance, skin, neck (including thyroid), eyes, ears, nose, throat, lungs, heart, abdomen, back, lymph nodes, extremities, vascular and neurological. Height and weight will be measured and recorded at screening.

Information for the physical examination will be included in the source documentation at the study site and will be recorded. Significant findings that are present at the screening visit will be recorded in the Medical History. Significant findings made after completion of any study procedure, which meet the definition of an AE, will be recorded.

# 6. SAFETY REPORTING

## 6.1. Safety/Adverse Events

Site Investigators and coordinators will be instructed to assess for AEs at in-person study visits when DaTSCANTM SPECT imaging, LP, skin biopsies, colon biopsies and submandibular gland biopsies are performed. AEs are also assessed by follow-up phone call at 7 days (±2 days) following all of these procedures.

Each subject must be carefully monitored for AEs. An assessment must be made of the seriousness, intensity, and relationship to the study procedure.

Procedure	Assessed through visit	7 day (±2 days) telephone contact
Dopamine Transporter SPECT Imaging	Х	Х
Lumbar Puncture	Х	Х
Skin Biopsies	Х	Х
Colon Biopsies	Х	Х
Submandibular Gland Biopsies	Х	Х

See table below for adverse event reporting periods:

# 6.2. Adverse Event Definitions

It is the responsibility of the Site Investigator to document any AE that occurs during the reporting periods listed above in the study. An AE includes any noxious, pathological, or unintended change in anatomical, physiological, or metabolic functions as indicated by physical signs or symptoms occurring in any phase of the clinical study whether or not associated with the study procedures and whether or not considered related to the study procedures. This definition includes an exacerbation of pre-existing medical conditions or events, historical conditions not present prior to study treatment, which reappear following study treatment, intercurrent illnesses, hypersensitivity reactions, drug interaction, or the significant worsening of the disease under investigation that is not recorded elsewhere in the case report form (CRF). Anticipated day-to-day fluctuations of pre-existing conditions that do not represent a clinically significant exacerbation or worsening need not be considered AEs.

AEs during the reporting periods, whether observed by the Site Investigator, elicited from or volunteered by the subject, should be recorded on the AE Log and submitted to the CTSDMC via the Online AE Reporting System (AERS). This will include a brief description of the experience, the date of onset, the date of resolution, the severity, and seriousness and whether the event was related to a specific procedure or participation in this study.

AEs should not be solicited with leading questions that suggest specific signs or symptoms. Rather, AEs should be solicited by asking the subject a non-leading question such as: "Do you feel different in any way since undergoing the study procedure or since the last assessment?"

The Site Investigator will evaluate all AEs with regard to the maximum intensity and relationship to study procedures, as follows:

### Maximum intensity

Maximum intensity should be assigned using 1 of the following 5 severity grades:

- Mild: aware of event but easily tolerated (Grade I)
- Moderate: discomfort, enough to cause interference with usual activity (Grade II)
- Severe: incapacitating: subject unable to work or perform usual activities (Grade III)
- Life-threatening (Grade IV)
- Death (Grade V)

### Relationship to study procedure

The following will guide the judgment regarding the causality of an AE and determination if the AE is study procedure-related:

Not Related:

- Not Related -- Improbable temporal relationship and is plausibly related to concomitant drugs or underlying disease
- Unlikely: Occurred within a reasonable timeframe after study procedure, but there is a likely association of an intercurrent/underlying medical condition or concomitant drugs

### Related:

- Possible Occurred within a reasonable timeframe after study procedure, but could be related to concomitant drugs or underlying disease
- Probably Occurred within a reasonable timeframe after study procedure, is unlikely to be attributable to concomitant drugs or underlying disease, and there is a plausible mechanism to implicate the study procedure
- Definite Occurred within a reasonable timeframe after study procedure and cannot be explained by concomitant drugs or underlying disease

The degree of certainty with which an AE is attributed to the study procedures or alternative causes (e.g., natural history of the underlying diseases, concomitant therapy, etc.) will be determined by how well the event can be understood in terms of known effects of the procedures and/or reaction of similar nature being previously observed with the specific procedure in question.

Any AE ongoing at the final 7 days ( $\pm 2$  days) reporting telephone visit should be followed until resolution, but not more than 30 days following study participation.

### 6.3. Serious Adverse Events

An SAE is an AE that is fatal or life-threatening, or results in hospitalization, prolongation of hospitalization, persistent or significant disability/incapacity, or a congenital anomaly/birth defect. A life-threatening AE is an AE that, in the view of the Site Investigator, places the subject at immediate risk of death from the reaction, as it occurred. Important medical events that may not result in death, be life-threatening, or require hospitalization may be considered an SAE when, based upon appropriate medical judgment, they may jeopardize the subject and may require medical or surgical intervention to prevent one of the outcomes listed in this definition.

Inpatient admission in the absence of a precipitating, procedure-related clinical adverse event is not subject to immediate reporting. For example:

- Admission for treatment of a pre-existing condition not associated with the development of a new AE
- Social admission (e.g., subject has no place to sleep)
- Protocol-specific admission during a clinical study (e.g., for a procedure required by another study protocol)
- Optional admission not associated with a precipitating clinical AE (e.g., for elective cosmetic surgery)

Inpatient admission does not include the following:

- Emergency Room/Accident and Emergency/Casualty Department visits
- Outpatient/same-day/ambulatory procedures
- Observation/short-stay units
- Rehabilitation facilities
- Hospice facilities
- Respite care (e.g., caregiver relief)
- Skilled nursing facilities
- Nursing homes
- Custodial care facilities

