### 6.4. Recording of Adverse Events

AEs, whether observed by the Site Investigator, elicited from or volunteered by the subject, should be recorded on the AE Log and reported to the CTSDMC via AERS. AEs are to be submitted to the CTSDMC within 5 working days of the site becoming aware of the event. This will include a brief description of the experience, the date of onset, the date of resolution, the severity, and seriousness and whether the event was related to a specific procedure (procedure-related) in the research study.

Any AE ongoing at the final 7 days ( $\pm 2$  days) reporting telephone visit should be followed until resolution or stabilization, but not more than 30 days from completion of the last study procedure.

The Independent Medical Monitor (IMM) for this study will review all AEs in aggregate on a quarterly basis. The CTSDMC will provide quarterly reports to the IMM and request an evaluation. Any trends or events of concern will be provided to the Site Investigator and to the Sponsor.

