### 6.5. **Responsibilities for reporting Serious Adverse Events**

- The Site Investigator will submit to the CTSDMC an AE Form through the AERS within 24 hours of his/her becoming aware of the occurrence of a SAE. The CTSDMC Project Manager will review the SAE and forward to the IMM for review.
- The following information should be supplied if available at the time of submission of the SAE study number, site number, subject number, subject age and gender, date of onset of event, event description, whether event required treatment, death and autopsy report, an identification of which criteria for a serious experience have been met, the Site Investigator's current opinion of the relationship between the event and study participation.
- The IMM will review the SAE within 2 working days of submission. The IMM will review whether the event meets the criteria for seriousness, relatedness, and expectedness. If needed, the IMM may consult with experts in the specific procedures for additional information regarding the procedures.
- The Site Investigator will comply with his/her local IRB and Radiation Safety Committee regulations regarding the reporting of AEs.

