### 7. **REPORTABLE EVENTS**

The following incidents will be considered reportable events and will be reported to the CTSDMC within 24 hours of the event, or the Site Investigator's knowledge of the event.

- Change of clinical diagnosis
- Participation in an interventional/therapeutic clinical trial
- Premature withdrawal (e.g. withdrawal of consent)
- SAE
- Unanticipated problems that are not AEs
- Pregnancy (reported by female subject or female partner of a male subject)
- Death

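### Section 6.3 exempts admissions from immediate reporting unless the adverse event is procedure-related, against the cause-neutral SAE definition and the 24-hour SAE deadline in 6.5 and Section 7

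*Protocol*

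**What the plan says.** Adverse events are defined without reference to cause. Protocol 5.1.15.2 takes in any untoward occurrence "without regard to the possibility of a causal relationship", and 6.2 repeats the point: "whether or not considered related to the study procedures". Section 6.3 builds the SAE definition on this and adds no causality condition, so an adverse event that results in hospitalization is an SAE.

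Two sections set the deadline for SAEs. Section 6.5 requires the form "within 24 hours of his/her becoming aware of the occurrence of a SAE". Section 7 lists SAE, without qualification, among the incidents that "will be reported to the CTSDMC within 24 hours of the event" or of the investigator's knowledge of it. In 6.5 the investigator's "current opinion of the relationship between the event and study participation" is one of the items to supply with the report, if available. It is not a condition for sending it.

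The second paragraph of 6.3 then reads: "Inpatient admission in the absence of a precipitating, procedure-related clinical adverse event is not subject to immediate reporting". Four examples follow: treatment of a pre-existing condition with no new adverse event, social admission, admission required by a protocol, and optional admission with no precipitating clinical adverse event.

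The only other submission deadline for adverse events is in 6.4: "AEs are to be submitted to the CTSDMC within 5 working days of the site becoming aware of the event".

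**The concern.** The exemption depends on a causality judgment that the rest of the safety chapter keeps out of the reporting decision. Under 6.5 the site gives its opinion on relatedness with the report, and the Independent Medical Monitor (IMM) then reviews seriousness, relatedness and expectedness. Under the 6.3 sentence the site's unreviewed opinion decides how soon the IMM sees the event.

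The exempt group is not confined to remote events. The rating that counts as not related includes: "Unlikely: Occurred within a reasonable timeframe after study procedure, but there is a likely association of an intercurrent/underlying medical condition or concomitant drugs". An infection after a lumbar puncture or biopsy that is first put down to intercurrent illness could be rated this way, and sections 9.2 and 9.4 to 9.6 list infection as a risk of those procedures. Subjects undergo several invasive procedures within 120 days of screening, in whatever order suits scheduling (3.1), so a late review could fall after the subject's next procedure. Sites that rely on different sections could also file the same kind of admission to different deadlines.

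**Working it through.** **Test case.** A subject is admitted with pneumonia during a reporting period. The site rates it unlikely to be related, and no other SAE criterion is met.

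| Provision | Result |
|---|---|
| 5.1.15.2 and 6.2, adverse event definition | Adverse event, whatever the cause |
| 6.3, SAE definition | SAE, because it led to hospitalization |
| 6.2, relationship categories | Falls under not related |
| 6.5 and Section 7 | Due at the CTSDMC within 24 hours |
| 6.3, exemption sentence | Not subject to immediate reporting |
| 6.4 | The remaining deadline, 5 working days |

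The protocol does not define immediate reporting, but 24 hours is its only expedited deadline for SAEs. One event therefore has two deadlines, and nothing in the protocol reconciles them.

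**The examples.** None of the four is an admission caused by a new adverse event. The last speaks of a precipitating clinical adverse event without the qualifier 'procedure-related'. The rule is therefore worded more widely than its own illustrations.

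**Length of the delay.** Inputs: 24 hours from awareness (6.5), 5 working days from awareness (6.4), and IMM review within 2 working days of submission (6.5). Assumptions: Monday-to-Friday working week, no holidays, every deadline used in full. Day 0 is the day the site becomes aware.

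- Path A (6.5): submission on day 1; review 2 working days later.
- Path B (6.3 with 6.4): submission after 5 working days; review 2 working days later.
- Delay = day under B minus day under A.

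| Awareness | Submission A / B | Delay | Review A / B | Delay |
|---|---|---|---|---|
| Mon | 1 / 7 | 6 | 3 / 9 | 6 |
| Tue | 1 / 7 | 6 | 3 / 9 | 6 |
| Wed | 1 / 7 | 6 | 5 / 9 | 4 |
| Thu | 1 / 7 | 6 | 5 / 11 | 6 |
| Fri | 1 / 7 | 6 | 4 / 11 | 7 |
| Sat | 1 / 6 | 5 | 3 / 10 | 7 |
| Sun | 1 / 5 | 4 | 3 / 9 | 6 |

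For example, with awareness on Friday, path A submits on Saturday (day 1) and the two working days end on Tuesday (day 4). Path B submits the next Friday (day 7) and review ends the Tuesday after that (day 11): 11 − 4 = 7 days.

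Submission is thus 4 to 6 calendar days later. Review falls on day 9 to 11 instead of day 3 to 5, which is 4 to 7 days later depending on the weekday. No event rate is assumed, because the protocol gives none.

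**The case against.** The strongest reply is that 6.3 waives only the timing and leaves SAE status alone. Since the admission remains an SAE, 6.5 and Section 7 still apply on their own terms, and 6.3 never points to 6.4. A site that reads the whole chapter has good reason to file within 24 hours, and the examples suggest that only admissions without a new event were meant. On this view the sentence is loosely worded and does little harm.

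Part of this stands. The direct clash is with the deadlines; the SAE definition matters because it brings unrelated admissions under them. The 5-working-day route is an inference, and the delay is a maximum on one reading. But the examples illustrate the sentence and do not limit it, and a site that follows it literally is following the protocol. If a deliberate exception was intended, 6.5 and Section 7 lack it. The text needs correcting on either reading.

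The exposed set is also small. Adverse events are collected for 7 days (±2) after five kinds of procedure. A rating of possible already counts as related, and admissions that meet another SAE criterion, such as a life-threatening event, are outside the argument. The entry under 6.4 must still state seriousness, and the SAE still goes to the IMM. The safety analysis in 10.4.2 rests mainly on the frequency of procedure-related events, which reporting speed does not change. All of this limits the size of the problem without removing the contradiction.

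**Conclusion.** The concern holds. For an admission caused by a new adverse event that the site rates as unrelated, 6.3 gives a different answer from 6.5 and Section 7, and no other text settles which applies. If a site follows 6.3 and falls back on 6.4, the IMM's review comes up to 4 to 7 calendar days later, depending on the weekday and assuming every deadline is used in full. Events are delayed, not lost. The number affected cannot be derived from the protocol and is probably small. The point concerns timely safety oversight only. The correction should be made, because the deadline for an SAE should not depend on a causality rating that the IMM has yet to review.

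**What to change.** In 6.3, delete the word 'procedure-related' and the comma before it. The exemption then covers only admissions with no precipitating clinical adverse event. That agrees with the four examples, the SAE definition, 6.5 and Section 7, and social, protocol-specific, optional and pre-existing-condition admissions without a new event stay exempt. The cost is one word and its comma, and possibly a few more 24-hour reports from sites.
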